### **3.3.5 VZV IFN- $\gamma$ ELISPOT**

Approximately 1000 patients from select study sites will be enrolled in the ELISPOT substudy and will have blood samples collected for exploratory purposes to assess for lymphocyte stimulation response to VZV antigen as measured by VZV-specific IFN- $\gamma$  ELISPOT. The blood samples will be collected for IFN- $\gamma$  ELISPOT on Day 1 (prior to Dose 1) and at Visit 5 (~28 days Postdose 4). The first 500 patients with STM and the first 500 patients with HM at participating sites will be enrolled into the study. Approximately 60-mL of blood will be collected into tubes containing EDTA or sodium heparin for isolation of PBMCs. Blood samples will be sent to a laboratory qualified in the Merck PBMC procedure for isolation and freezing of PBMCs. The isolated PBMCs will be tested by VZV-specific IFN- $\gamma$  ELISPOT assay at a central laboratory.

The purpose of the VZV ELISPOT assay is to detect interferon gamma (IFN- $\gamma$ ) secreting VZV-specific cells from PBMCs before and after vaccination with VZV-containing vaccine(s). This assay is performed by IBT Laboratories to evaluate the cellular immune response to the vaccine(s). Results for the assay are expressed as the frequency of spot forming cells (SFCs) per million PBMCs.

The IFN- $\gamma$  ELISPOT assay utilizes 2 high-affinity IFN- $\gamma$  specific monoclonal antibodies that are directed against different epitopes on the IFN- $\gamma$  molecule. In the VZV-specific IFN- $\gamma$  ELISPOT assay,  $5 \times 10^5$  PBMCs are stimulated by VZV antigen in wells of cell culture plates that have been precoated with one mouse monoclonal antibody to human IFN- $\gamma$ . IFN- $\gamma$  released by the VZV-specific T-cells then binds to the first antibody present in close proximity to the cells that produced it. After ~18 hours in culture, the cells are washed away, and a biotinylated form of the second antibody to IFN- $\gamma$  is added to the wells of the plate and incubated overnight at 4°C. The plates are washed and then alkaline phosphatase-streptavidin is added to each well of the plate. After 2 hours of incubation at room temperature, the plates are washed again and a chromogenic substrate (NBT/BCIP) is added to react with the alkaline phosphatase. As a result, dark blue spots develop against the white background of the plates. The IFN- $\gamma$  produced by each cell results in the formation of a spot on the culture plate and the number of spots approximates the number of cells that produced IFN- $\gamma$  in response to VZV antigen. The frequency of SFCs is usually expressed per million input PBMCs. This reflects the T-cell precursor frequency specific to VZV circulating in the blood at a defined time point. The source of antigen used to stimulate VZV-specific responses is a UV-inactivated virus stock of the Oka/Merck vaccine strain that was produced in MRC-5 cells. A similar preparation from uninfected MRC-5 cells is used as the negative control.

Patients in the ELISPOT substudy will have a separate allocation schedule to assure a well-balanced randomization ratio.

### **3.4 SAFETY MEASUREMENTS**

#### **3.4.1 Clinical Measurements for Safety/Vaccination Report Card**

##### **3.4.1.1 Safety Follow-up During the Vaccination Period**

Each patient will receive a VRC at Visits 1, 2, 3, and 4. On the VRC, patients will be asked to record daily oral temperature measurements on the VRC. Patients should take oral temperature measurements using only the SPONSOR provided standard oral thermometer. Temperature measurements via the otic or axillary methods are not permitted. Patients will also be asked to record on the VRC all adverse experiences during the primary safety follow-up period (postvaccination dose 1 through 28 days postvaccination dose 4), including injection-site adverse experiences and systemic adverse experiences occurring from Day 1 through 28 days postvaccination dose 4. Patients will be asked to record on the VRC any rash at the injection site, as well as any varicella/varicella-like or HZ/HZ-like rashes postvaccination Day 1 through 28 days postvaccination dose 4. Any vaccines other than study vaccines and any medications that are administered during that period should also be documented on the VRC.

The patient will be asked to bring the VRC to the study site at the next scheduled visit. Study personnel will review the VRC for completeness, accuracy, and clarity at each scheduled visit from Visit 2 through Visit 5. All comments are to be reviewed by study personnel and discussed with the patient for clarification, as necessary. Any information gained during VRC review with the patient should be clearly documented, initialed, and dated at the bottom of the VRC. The VRC is considered a source document and no original information recorded by the patient should be crossed out or altered in any manner by study personnel.

All VRC information will be recorded in the Electronic Data Capture (EDC) system. The physician investigator/sub-investigator will determine causality of systemic and injection site adverse experiences recorded on the VRC using the reporting guidelines given in the protocol (Table 3-1) and will classify each event as a SAE (SAE) or nonserious adverse experience (NSAE). If an oral temperature measurement indicates a fever (defined in this study as an oral temperature of  $\geq 100.4^{\circ}\text{F}$  or  $\geq 38.0^{\circ}\text{C}$ ), the adverse experience must be reported as such in the database. However, if the fever is a symptom of another reported adverse experience, a separate AE report of fever is not necessary. Refer to the eCRF entry guidelines for details related to AE reporting.

### **3.4.1.2 Post-Vaccination Safety Follow-up**

After the end of the vaccination period (i.e., 28 days postvaccination dose 4), patients will continue to be followed for SAE, regardless of causality, through the end of the study (see Section 3.4.6.1 for additional information on SAEs). Patients will be educated on the criteria for SAE and instructed to call the site immediately if a SAE occurs. In addition, every 3 months (+/- 1 month) beginning 3 months following Visit 5 through the duration of the study, patients will be contacted by study staff either at a scheduled study visit or by telephone, using a pre-specified script, to determine if the patient had a previously unreported clinical adverse experience that met SAE criteria and collect relevant information on SAEs. SAE will be collected as described in Section 3.4.5.1.

In the event the study is terminated sooner than 1 year after the last vaccine dose is administered in this study, the study will continue to allow all patients to complete at least a 1 year post-vaccination safety and efficacy follow-up (including new cases of HZ in these patients).

### **3.4.1.3 Adverse Experience Toxicity Grading**

A vaccine specific toxicity grading scale (Grades 1 through 4) will be applied to all serious and non-serious adverse experiences in this study. During the primary safety follow-up period (through ~28 days postvaccination dose 4), clinical adverse experiences will be recorded on the VRC by the patient at the time of occurrence. The investigator will use the information provided by the patient both on the VRC, and verbally at the time of VRC review, to apply the appropriate toxicity grade (1 through 4). Serious adverse experiences occurring beyond ~28 days postvaccination dose 4 are *not reported* on the VRC. For these events, the investigator will assign the toxicity grade based upon information received at the initial report (and/or subsequent follow-up) of the event. The grade assigned by the investigator will be recorded in the electronic database on the corresponding eCRF. Refer to Appendix 6.2 for Toxicity Grading Tables for injection-site and systemic AEs, respectively.

This adverse experience toxicity grading is in addition to the grading of adverse experiences by maximum intensity (mild, moderate, severe) described in Table 3-1.

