## **2. CORE PROTOCOL**

### **2.1 OBJECTIVES AND HYPOTHESES**

#### **2.1.1 Primary Objectives**

1. To assess the safety and tolerability of V212 when administered to adults with STM .
2. To assess the impact of V212 on the development of HZ in adults with STM.

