## **2.2 PATIENT INCLUSION CRITERIA**

An individual will be eligible to participate in this study if all of the following criteria apply:

1. Patient has been diagnosed with a solid tumor or hematologic malignancy AND is not likely to undergo hematopoietic cell transplant (HCT) and meets one of the criteria specified below.
  - Is 18 years of age or older and is receiving a cytotoxic or immunosuppressive chemotherapy regimen.

OR

- Is 50 years of age or older\* with a hematologic malignancy, not in remission, regardless of whether the patient is or is not receiving chemotherapy.

\* **Note: In India only, enrollment is restricted to patients 18 to 65 years of age.**

2. Life expectancy  $\geq$  12 months.
3. Signed an informed consent prior to any study procedures.
4. Patient has prior history of varicella, antibodies to VZV (documented prior to receipt of blood products), or residence (for  $\geq$ 30 years) in a country with endemic VZV infection, or if participant is <30 years old, attended primary or secondary school in a country with endemic VZV infection (see Section 3.2.8 for more details).
5. All female patients of childbearing potential (as defined below under #7) must have a negative serum or urine pregnancy test (sensitive to 25IU  $\beta$ -hCG).
6. Able to understand and complete study questionnaires.
7. Patient is highly unlikely to conceive during the time period starting 2 weeks prior to enrollment through 6 months from last vaccination dose, as indicated by at least one “yes” answer to the following questions:
  - Patient is male.
  - Patient is female who agrees to remain abstinent or use (or have their partner use) adequate contraception during the time period starting 2 weeks prior to enrollment through 6 months from the last vaccination dose. Note that simultaneous use of two reliable forms of contraception is recommended.
  - Patient is a female who is not of reproductive potential. A female patient who is not of reproductive potential is defined as: one who has either (1) reached natural menopause (defined as 6 months of spontaneous amenorrhea with serum follicle stimulating hormone [FSH] levels in the postmenopausal range as determined by a laboratory, or 12 months of spontaneous amenorrhea), (2) post-surgical bilateral oophorectomy and/or hysterectomy, or (3) bilateral tubal ligation.

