### **3.4.6 Evaluating Adverse Experiences**

Refer to Table 3-1 for instructions in evaluating adverse experiences.

Table 3-1

An investigator who is a qualified physician, will evaluate all adverse experiences as to:

Maximum Intensity	Mild	awareness of sign or symptom, but easily tolerated (for pediatric studies, awareness of symptom, but easily tolerated)						
	Moderate	discomfort enough to cause interference with usual activity (for pediatric studies, definitely acting like something is wrong)						
	Severe	incapacitating with inability to work or do usual activity (for pediatric studies, extremely distressed or unable to do usual activities) Injection site redness or swelling from the day of vaccination through Day 5 post-vacc will be evaluated by maximum size.						

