### **3.5.5.3 Analysis of Vaccine Safety**

The safety follow-up period will occur for at least 1 year following the last VZV vaccination. Safety and tolerability of V212 will be assessed by evaluation of all relevant safety parameters, focusing on the 28-day follow-up period after any vaccination. The following safety analyses will be evaluated for the HM and STM populations separately.

The primary safety endpoint of the study will be based on the incidence of SAEs observed during the period up to 28 days Postdose 4 in each vaccination group. Two-sided 95% CI on the proportion of any SAE will be provided for each vaccination group based on the exact binomial distribution [19]. To provide an overall assessment, safety measures such as the proportion of patients with (1) any adverse experience, (2) any injection-site adverse experience, (3) any systemic adverse experience, (4) any SAE, (5) any vaccine-related SAE, and (6) any discontinuation due to an adverse experience will be summarized for both vaccination groups (across any vaccination dosing period and by each vaccination dosing period). The risk differences on these overall safety parameters between the two groups and the corresponding two-sided 95% CI on the risk difference will be provided using the stratified asymptotic methods proposed by Miettinen and Nurminen [20].

To assess the risks of the adverse experiences temporally associated with vaccination, a multi-tiered approach will be used for the analysis of specific safety parameters.

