For Tier-1 adverse experiences, risk differences between the two groups, corresponding two-sided 95% CI on the risk difference, and the p-value for the test of significant risk difference will be provided. The corresponding p-value will be based on the normal approximation for testing two independent binomial proportions at the two-sided 0.05 level adjusting for stratification factors. The risk difference and 95% CI will be calculated using the methods proposed by Miettinen and Nurminen [20]. Tier 1 adverse experiences include (1) systemic adverse experiences prompted for on the VRC, including varicella/varicella-like or an HZ/HZ-like rash occurring after any study vaccination through 28 days Postdose 4, (2) injection-site complaints prompted for on the VRC, such as redness, swelling, and pain/tenderness/soreness occurring Day 1 through Day 5 after any vaccination, and (3) elevated temperature ( $\geq 100.4^{\circ}\text{F}$  [ $\geq 38.0^{\circ}\text{C}$ ]), after any study vaccination through 28 days Postdose 4.

Additional summaries on Tier-1 safety parameters will also be provided by the dosing period..

For Tier-2 adverse experiences, risk differences between the two groups and the corresponding two-sided 95% CI on the risk difference will be provided using the methods proposed by Miettinen and Nurminen. This Tier-2 approach will be applied to the proportions of any other injection-site adverse experiences or systemic adverse experiences after any study vaccination through 28 days Postdose 4 that are not prompted for on the VRC but occurred in at least 1% of the patients in either treatment group.

Additional summaries on Tier-2 safety parameters will also be provided by the dosing period, and gender in each vaccination group.

Tier 3 adverse experiences will include summaries for any other adverse experiences after any study vaccination through 28 days Postdose 4.

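### Severity of adverse experiences is recorded three ways, but no severity-based comparison between arms is pre-specified, so a mild-to-severe shift in non-serious reactions could go unseen

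*Combined protocol and SAP*

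**What the plan says.** **Objective and population.** The first primary objective (2.1.1) is "To assess the safety and tolerability of V212 when administered to adults with STM". Under 2.2, a patient with a solid tumor qualifies if he or she "is receiving a cytotoxic or immunosuppressive chemotherapy regimen".

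**What is recorded.** Section 3.4.1.3 says "A vaccine specific toxicity grading scale (Grades 1 through 4) will be applied to all serious and non-serious adverse experiences in this study", and that the grade goes into the database on the eCRF. It adds that this is on top of the mild, moderate or severe intensity rating in Table 3-1. Under that table (3.4.6), "Injection site redness or swelling from the day of vaccination through Day 5 post-vacc will be evaluated by maximum size". Appendix 6.2 defines the grades: Table 6-5 for injection-site events, Table 6-6 for systemic events.

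**What is analysed.** Section 3.5.5.3 opens with "Safety and tolerability of V212 will be assessed by evaluation of all relevant safety parameters". For the overall assessment it lists "safety measures such as the proportion of patients with (1) any adverse experience, (2) any injection-site adverse experience", then any systemic event, any SAE, any vaccine-related SAE and any discontinuation due to an adverse experience. Tier 1 covers prompted systemic events, prompted injection-site complaints and elevated temperature. These get "risk differences between the two groups, corresponding two-sided 95% CI on the risk difference, and the p-value for the test of significant risk difference". Tier 2 covers unprompted events seen in at least 1% of either arm and gets risk differences with intervals. Tier 3 gets unspecified summaries. As for breakdowns, "Additional summaries on Tier-1 safety parameters will also be provided by the dosing period"; Tier 2 is also split by gender, and SAEs and Tier 1 events by body system. Sections 2.7.3 and 3.5.3.3 match this. The interim safety analysis in 3.5.8.2 refers back to 3.5.5.3.

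**The concern.** Tolerability is half of a primary objective, and for a four-dose regimen it depends on how bad reactions are as well as how many patients have one. The planned comparisons treat each term as present or absent. A patient whose injection-site pain needs a narcotic or stops daily activity (Grade 3) counts the same as one whose pain does not interfere with activity (Grade 1).

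If the vaccine turned mild reactions into severe ones in patients who would have reported the term in any case, the proportion with the term would be equal in the two arms and the planned risk difference would be near zero.

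There is also a pre-specification issue. Two overlapping severity scales are in use, and Grade 3 means different things for injection-site and systemic events. A severity analysis chosen only after unblinding would leave the definition of severe open to choice.

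**Working it through.** **1. Collection set against analysis.**

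| Severity item | Where recorded | Named in 2.7.3, 3.5.3.3 or 3.5.5.3? |
|---|---|---|
| Toxicity grade 1 to 4 | 3.4.1.3, Tables 6-5 and 6-6 | No |
| Maximum intensity | 3.4.1.3, Table 3-1 | No |
| Size of redness or swelling, Day 1 to 5 | Table 3-1, Table 6-5 | No |

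Elevated temperature in Tier 1 is a single threshold at 38.0°C, so it also measures occurrence.

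**2. What the occurrence analyses already pick up.** Three routes bring some severe events in.
- Table 3-1 makes an event serious if it is fatal, life-threatening, significantly disabling or leads to inpatient admission, and allows other important medical events to be judged serious.
- Discontinuation due to an adverse experience is compared.
- Section 3.4.2 counts a clinically significant increase in the frequency or intensity of a preexisting condition as an adverse experience, so such a worsening enters the incidence count.

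What is left is the non-serious, non-discontinuing reaction that is new after vaccination. Injection-site reactions fit this description best. Injection-site Grade 3 is narcotic use or prevented daily activity (size E for Day 1 to 5 redness or swelling), which need not be serious. Systemic Grade 3 requires both prevented daily activity and medical intervention, so it overlaps more with the SAE definition, to an extent the documents do not quantify.

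**3. The plan's own precision figures.** Table 3-4 in 3.5.7.2 uses n = 1348 per arm and two-sided 0.05. With p̄ the mean of p1 and p2, S0 = √(2p̄(1−p̄)/n) and S1 = √([p1(1−p1) + p2(1−p2)]/n):

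power = Φ((|p2 − p1| − 1.96·S0)/S1)

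For 1% v 2.39%: S0 = 0.00497, S1 = 0.00496, (0.0139 − 1.96 × 0.00497)/0.00496 = 0.837 (unrounded inputs), power 79.9%. All eight rows give 79.5% to 79.9%, so the table reproduces.

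**4. What a Grade 3 or higher comparison would offer.** The same formula, with assumed base rates of patients with a Grade 3 or higher event (the documents give none). The half-width of the 95% CI is 1.96·√(2p(1−p)/n) at base p.

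| Assumed base | Power for a 1.39-point excess | Excess detectable with ~80% power (Table 3-4) | CI half-width |
|---|---|---|---|
| 1% | 79.9% | 1.39 points | 0.75 points |
| 5% | 34.3% | 2.61 points | 1.65 points |
| 10% | 21.4% | 3.45 points | 2.26 points |
| 20% | 14.2% | 4.46 points | 3.02 points |

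Table 3-4 puts the lower rate in the vaccine group; the power is the same either way round.

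**5. Occurrence and grade compared at the same excess.** Assume 20% of each arm report a term, with Grade 3 or higher in 0.5% of one arm and 2.0% of the other, an excess of 1.5 points.
- *Pure shift.* Occurrence is 20% in both arms, so the occurrence test rejects only at its 5% false-positive rate. The graded comparison has (0.015 − 1.96 × 0.00428)/0.00427 = 1.549, power 93.9%.
- *Wholly additional reporters.* Occurrence is 20% v 21.5%, and the occurrence test has 15.9% power.

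The pure-shift result for occurrence follows from the definitions and needs no rate. The 93.9% depends on severe events being rare.

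**The case against.** The analysis lists are open. Section 3.5.5.3 promises all relevant safety parameters, introduces its measures as examples, and leaves Tier 3 and the detail of the SAE listings unspecified. A reader might infer from the silence that severity will not be reported, or that the sponsor chose to leave it out. The documents do not support that: a routine table by grade is compatible with the text. What stands is narrower. An open phrase fixes no cut-point, window or comparison, and section 3.5 rules out a separate SAP where these could be found. The DMC guidelines are a separate document that is not available here, but 3.5.8.2 points the interim safety analysis back to 3.5.5.3.

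A second objection is that severe events are already compared. In part they are, through the three routes in step 2 of the working. So the reading that severe reactions go uncompared altogether is also too strong. None of those routes reliably captures a new, non-serious Grade 3 injection-site reaction.

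Third, the benefit is uncertain. Every severe-event rate is an assumption, and power for a 1.39-point excess is about 34% or less once the base reaches 5%. That holds, and it limits the claim for systemic events in patients on chemotherapy, where the base may be higher. Even so, an estimate with an interval would be informative where none is planned.

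**Conclusion.** The point holds as a minor gap in pre-specification. Severity is recorded in three forms, the planned comparisons rest on occurrence, and a mild-to-severe shift in non-serious reactions among patients who would report the term anyway would not appear in them. The exceptions are events that become SAEs, lead to discontinuation or count as worsening of a preexisting condition.

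The textual part rests on the protocol alone. The gain from a graded comparison cannot be fixed: for a 1.39-point excess it runs from 80% power at an assumed 1% base to 14% at 20%. It is likely to be largest for injection-site reactions, if severe ones are uncommon.

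A reader might infer that the trial will miss a severe reactogenicity signal. The documents do not show that, because they give no severe-event rate and no evidence of a shift. The primary safety endpoint (SAEs), the sample size and the efficacy decision rule are untouched, and the data are retained.

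**What to change.** In 3.5.5.3, before final unblinding, add for the STM and HM populations separately:
- the proportion of patients with any Grade 3 or higher injection-site adverse experience (Table 6-5) through 28 days Postdose 4;
- the proportion with any Grade 3 or higher systemic adverse experience (Table 6-6) over the same period;
- for each, the between-group risk difference and 95% CI by the Miettinen-Nurminen method already in use;
- a table of VRC-prompted injection-site events by maximum grade or size, overall and by dose. It should show size A, which is reportable but has no grade.

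As an example of the output, with invented counts and no stratification, 32/1348 v 13/1348 gives a difference of 1.41 points (95% CI 0.46 to 2.46).

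The cost is a few lines of text and two or three tables from data already in the database. Section 3.5 allows changes to non-confirmatory analyses if the CSR records when and why. The downside is a few more unadjusted safety comparisons, which the caution in 3.5.6 already covers.
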